## 12.0 Study Timelines

*12.1 Describe the anticipated duration of the study needed to enroll all study subjects.*

The plan is to enroll all study participants in three months.

*12.2 Describe the duration of an individual subject's participation in the study. Include length of study visits, and overall study follow-up time.*

Each participant's time in the study will be 15 months +/- 4-8 weeks (depending on what point in the first trimester a participant begins)

*12.3 Describe the estimated duration for the investigators to complete this study (i.e. all data is collected and all analyses have been completed).*

The time from first recruitment to wrap up of this phase of the project is estimated to be 22 months.

## 13.0 Research Setting

*13.1 Describe all facilities/sites/locations where you will be screening and conducting research procedures. Include a description of the security and privacy of the facilities (e.g. locked facility, limited access, privacy barriers). Facility, department, and type of room are relevant. Do not abbreviate facility names.*

*Example: "A classroom setting in the New Academic Building equipped with a computer with relevant survey administration software", "The angiogram suite at University Hospital downtown campus", The Clinical Research Unit in the Institute for Human Performance."*

The second floor of the Institute for Human Performance (private room as needed for evaluation and/or exercise prescription and the physical therapy gym); individual participant's homes

*13.2 For research procedures being conducted, for this study, external to Upstate (e.g., in schools, out-of-state, internationally, etc.) describe:*

- *Site-specific regulations or customs affecting the research*
- *The composition and involvement of any community advisory board*
- *Local scientific and ethical review structure outside the organization.*
- *Local issues affecting the research and rights of research subjects.*

*NOTE: This question is not referring to multi-center research. If this research is being conducted internationally, Supplemental Form E must be completed and uploaded.*

- N/A: This study is not conducted outside of Upstate.

## **14.0 Resources and Qualifications**

*14.1 The Principal Investigator (PI) must confirm, in consultation with Chair and Dean as applicable, that adequate resources are present to conduct and complete the study compliantly and safely. Specifically:*

- The proposed subject population(s) are available in sufficient numbers to meet the study requirements*
- Sufficient funds are available to conduct and complete the study compliantly and safely*
- The PI and study team have sufficient time to conduct and complete the study compliantly and safely*
- The PI has determined that the named study team is qualified to conduct the research compliantly and to monitor the safety and welfare of the enrolled research subjects effectively*
- The PI ensures that the study team is fully aware of his/her involvement in this study and the details of the study protocol*
- The PI ensures that the study teams will only be involved in research procedures for which they have been trained, and are currently certified and/or licensed, if required.*

- Confirmed**

*14.2 Describe the availability of medical or psychological resources that subjects might need as a result of anticipated consequences of the research, if applicable. (e.g, “on-call availability of a counselor or psychologist for a study that screens subjects for depression”).*

Each participant’s OB/GYN and their emergency care contact will be immediately contacted in the event of any adverse events.

*14.3 Describe your process to ensure that all study team members are updated on the progress of the research and the regulatory requirements (including enrolled subjects, unanticipated problems etc.)*

[name] and [name] will be supervising the EX subjects training, fitness testing, collection of questionnaires in addition to the weekly contact of the HOMEEX subjects. In addition, [name] and [name] will be conducting all follow-up testing and home visits. Upstate DPT students and *Vitality Fitness* staff members will be used to help with the supervision of the EX subjects and testing of the EX, HOMEEX, and UC groups. Since [name] and [name] are directly supervising and testing subjects in this study, they will be aware of the research progress and any unanticipated problems which can be conveyed to the DPT students and *Vitality Fitness* staff. Any individuals assisting in the conduct of the study will be added to the registration form.

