## 4.0 Study Design

4.1 Describe and explain the study design (e.g. case-control, cross-sectional, experimental, interventional, longitudinal, and observational). Indicate if there is randomization, blinding, control group, etc. If randomizing, explain how this will be

*achieved. For studies that have a complex study design (i.e., multiple arms and treatments), include a schematic diagram.*

This is a pilot investigation (feasibility) of a future larger study of interventional design with randomization. Participants in the pilot phase of the project will be randomized using a free online research randomizer (randomizer.org).

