submaximal treadmill test to determine HRR for the two exercise groups and estimate VO2max using the Pollock equation which will be repeated at 3- and 6-months after birth to compare aerobic fitness levels.

All women will complete the following questionnaires at baseline (late 1st trimester), 25-26 weeks (late 2nd trimester), and 37-38 weeks (late 3rd trimester), and monthly through 6-months post-natal: MFI, SF-12 QOL; PSQLI; CES-D; EPDS; and the PPAQ. All questionnaires have been demonstrated to have good validity, reliability, and internal consistency and the CES-D and EPDS are similar to each other in regards to internal consistency and test-retest reliability.

Infants from mothers in all three groups will have their gross and fine motor, and cognitive development measured monthly (months 1-6) at home using the Bayley Scales of Motor Development, 4th edition. The Bayley 4 is a standardized, norm-referenced tool with subtest level scaled scores, domain level composite scores, percentile ranks, and developmental age equivalents. Infant height and weight will be measured monthly through 6-months of age.

Women assigned to EX will have all of their supervised pregnancy exercise sessions, questionnaires, and weight measured at the IHP. After delivery, women assigned to EX will resume their supervised IHP exercise program between 4-8 weeks (depending on delivery mode) when they are cleared for activity by their physician, complete exercise testing at 3- and 6-months and will have monthly home visits for infant testing through 6 months. HOMEEX and UC women will visit the IHP at baseline, 3 & 6-months post-delivery for exercise testing, questionnaires, and weight measurement. HOMEX and UC groups will receive home visits for: 2nd & 3rd trimester questionnaires and weight measurement and every month post-delivery for questionnaires, weight measurement and infant testing.

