While we will not be analyzing the data (e.g. results of depression or other questionnaires) during the study to avoid compromising interactions (e.g. bias) with participants, study personnel will be speaking to participants in the HOMEEX and EX groups multiple times per week. Participants will be asked about their next OB/GYN appointment and if anything about their health status has changed (this helps to also insure that each participant is maintaining an active relationship with her OB provider). The physician approval form that provides a participant with clearance to participate in the study will include a statement that asks the physician to inform study personnel immediately if the participant develops any contraindication, relative or absolute, to participation in an exercise program (e.g. fetal growth restriction or gestational hypertensive disorder). Gestational diabetes mellitus (GDM) will be handled per individual participant's OB/GYN recommendations. If a participant develops an absolute contraindication to participation in the study, they will be removed from the study. If a participant experiences an adverse event, a new clearance must be provided by OB/GYN for the participant to return to the study. In the case of an emergency, participants will be advised to seek care at Upstate Community Hospital. If a participant needs NICU care, they will be advised to seek care at Crouse or St. Joseph's hospital.

Only full term infants (birth at 37+ weeks gestation) will go on to participate in the neonatal portion of the study. Infants participating in this portion of the study will undergo monthly height, weight, motor and cognitive assessments that pose minimal to no risk to the infant. In the

event, that an assessment uncovers unexpected information (e.g. loss of weight, significantly delayed motor development), participants will be advised to contact their pediatrician.

Participants will regularly be asked how they are feeling. If a participant expresses that she is feeling blue or is having depressive thoughts, study personnel will recommend that she contact her health provider. We will follow up each week to check the status of these symptoms and to make sure they have spoken with their health provider. Participants in the control group are also being contacted weekly, so relationships are being established, and the same process for experiencing undesirable thoughts or feelings would apply.

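### The people who coach the exercise arms appear also to run the postnatal treadmill and infant tests, with no rule separating coaching from assessment

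*Combined protocol and SAP*

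**What the plan says.** Section 14.3 assigns the work. Two named members "will be supervising the EX subjects training, fitness testing, collection of questionnaires in addition to the weekly contact of the HOMEEX subjects". The next sentence says that two named members "will be conducting all follow-up testing and home visits". The section's closing remark gives one pair both roles: they "are directly supervising and testing subjects in this study". Physical therapy students and fitness staff "will be used to help with the supervision of the EX subjects and testing of the EX, HOMEEX, and UC groups".

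Section 11.0 says which outcomes these people would measure. For the Bayley: "Infants from mothers in all three groups will have their gross and fine motor, and cognitive development measured monthly (months 1-6) at home". For fitness, VO2max is estimated from a submaximal treadmill test "using the Pollock equation which will be repeated at 3- and 6-months after birth to compare aerobic fitness levels".

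Section 5.1 plans Kruskal-Wallis and Friedman tests for between-group and within-group differences in maternal and infant outcomes. Section 5.2 says that pilot data may be used in the power analysis of the larger study.

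The prompt in section 4.1 asks about blinding, but the answer covers only randomization. No other section describes a masked or independent assessor. The nearest safeguard is in section 19.4, where results are left unanalyzed during the study "to avoid compromising interactions (e.g. bias) with participants".

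**The concern.** An examiner scores the Bayley directly. The treadmill result comes from an equation, but a person conducts the test that feeds it. In either case a tester who has worked with the mother through pregnancy, and knows her arm, may record or conduct the test differently without meaning to. Planned contact is unequal: three supervised classes a week in EX, two contacts a week in HOMEEX and one reminder a week in the control group. A tester's lean therefore need not cancel between arms.

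At stake are the between-group comparisons of aerobic fitness, which is a named Aim 2 outcome, and of infant development, which section 5.1 adds. Any arm difference on these outcomes that was later carried into a power analysis would take the lean with it. The pilot is also the natural place to learn whether separate assessment is workable before the larger trial needs it.

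**Working it through.** The main check is a reading of the text. The arithmetic only gives scale.

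**1. Are they the same people?** The removed names mean that the identity of the two pairs cannot be read directly. The closing remark of section 14.3 attributes supervising and testing to one pair, so a single pair in both roles is the natural reading. The helpers are also described as doing both, so they do not supply an independent assessor as the text stands.

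**2. Who would have coached whom?**

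| Arm | Contact (section 11.0) | Tester has coached the mother? | Tester likely to know the arm? |
|---|---|---|---|
| EX | three supervised classes a week | yes | yes |
| HOMEEX | individual meeting, then contact twice a week | yes | yes |
| Control | weekly reminder; told to continue current activity | no | yes |

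Knowledge of the arm is an inference. It rests on the coaching roles and on home visits whose content differs by arm: section 11.0 adds questionnaires and weight to HOMEEX and control home visits, while EX home visits are for infant testing.

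**3. Which outcomes are exposed?** The Bayley (scored by the examiner) and the treadmill test (run by the examiner). The SF-12, MFI, sleep, depression and activity questionnaires are self-report, and masking an examiner would not change them in the same way.

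**4. How many assessments?** At the ceiling of 18 women, with full retention and all births at term: 18 × 6 = 108 Bayley assessments and 18 × 2 = 36 postnatal treadmill tests.

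**5. Could the data reveal a lean?** With 6 per arm, the standard error of a difference between two arms in SD units is √(1/6 + 1/6) = √(2/6) = 0.577. An assumed lean of 0.1, 0.2 or 0.3 SD is 0.1/0.577 = 0.17, 0.2/0.577 = 0.35 or 0.3/0.577 = 0.52 of one standard error. None of these could be told from chance.

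**6. Illustration only: what if an arm difference were used for planning?** The documents give no effect size and no lean. Assume a true difference of 0.4 SD, a two-sided 5% test and 80% power. The normal approximation is n per arm = 2(1.960 + 0.842)²/d² = 15.70/d², and the t-test adds about one per arm.

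| Assumed lean (SD) | Apparent d | 15.70/d² | t-test, per arm |
|---|---|---|---|
| 0 | 0.4 | 98.1 | 100 |
| 0.1 | 0.5 | 62.8 | 64 |
| 0.2 | 0.6 | 43.6 | 45 |
| 0.3 | 0.7 | 32.0 | 34 |

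Sampling error alone is larger than any of these leans. Around a true 0.4 SD, the 95% range of the pilot estimate is 0.4 ± 1.96 × 0.577, or about −0.7 to +1.5 SD.

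**The case against.** The strongest reply is that this is an 18-woman feasibility pilot. Section 2.1 makes feasibility and the suitability of the measures the endpoint. Aim 2 lists only maternal measures, nearly all self-reported, so the Bayley belongs to no aim. That stands, and it limits the weight of the point. It does not remove it, because aerobic fitness is in Aim 2 and section 5.1 plans group comparisons for infant outcomes too.

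A second reply is that sizing a trial on a difference from 6 per arm would be unsafe even with perfect masking. That is correct, as step 6 shows, and it is a reason to rule out that use in writing.

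A third is that masking would often fail: visit content differs by arm, and training and testing share the same floor of the institute (section 13.1). This also stands. It is why the main remedy should be a rule that works without masking.

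A fourth is that baseline tests appear to follow allocation and would not be covered. But the baseline treadmill test sets the heart-rate range for the exercise programme, so coaching to that range should not have begun. The remaining exposure there is knowledge of the arm.

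Some stronger readings are tempting but not supported:
- A reader might infer that arm differences are intended for the power analysis, and hence that the larger trial will be too small. Section 5.2 only permits the use of pilot data and does not say which quantities.
- A reader might infer that every tester will have coached every mother. Control women are not coached.
- A reader might take section 19.4 as showing that the plan contradicts itself on bias. That section concerns knowledge of results during the study, not knowledge of the arm.
- Nothing in the documents describes how treadmill testers encourage or stop a woman, so no specific mechanism can be claimed there.

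**Conclusion.** The point holds as an inexpensive improvement. On its natural reading, section 14.3 has coaches performing the examiner-dependent postnatal tests in the two exercise arms, and testers who probably know the allocation in all three. No section separates the roles. The direction and size of any bias are unknown. With a standard error of about 0.58 SD, the pilot could neither detect nor exclude a lean of a few tenths of an SD. The planning figures above depend wholly on assumed values and are not a forecast.

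The conclusion rests on two inferences: that the removed names are one pair, and that people in these roles know the arm. It does not extend to the questionnaires in the same way, and it does not undermine the feasibility endpoints of recruitment, retention and adherence.

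**What to change.** 1. In section 14.3, state that nobody scores the Bayley or conducts the 3- or 6-month treadmill test of a woman she supervised or coached. Achieve this by dividing duties between the two leads, with the existing students and fitness staff. Let each assessor cover all three arms, so that assessor and arm are not confounded.
2. Align the text in sections 11.0 and 19.4 that lets either of two named members hold the individual HOMEEX meeting: whoever holds it does not later test that woman or her infant.
3. Where workable, do not tell the assessor the arm, have the coaching side collect the questionnaires and weight that make home visits differ by arm, and record the assessor's guess of the arm.
4. In section 5.1, state that masking will be partial, that between-group differences on the Bayley and the treadmill test are descriptive, and that they will not be used as effect-size inputs for the larger study.

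Cost: protocol wording and a duty roster, with no new procedures and no staff beyond those already in section 14.3. The documents give no staff hours, so the team should confirm that the roster covers up to 108 Bayley and 36 treadmill assessments. Scheduling becomes less flexible, and masking will still fail for some women.

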## 15.0 Provisions to Protect the Privacy Interests of Subjects

*15.1 Describe how you will protect subjects' privacy interests during the course of the research and any steps you will take to make the subject feel at ease.*

*NOTE: Privacy refers to an individual's desire/right to control access to or to place limits on whom they interact with or whom they provide personal information. Privacy applies to the person. Confidentiality refers to how data collected about individuals for the research will be protected by the researcher from release. Confidentiality applies to the data.*

*Examples of appropriate responses include: "participant only meets with a study coordinator in a private office setting where no one can overhear", or "the participant is reminded that they are free to refuse to answer any questions that they do not feel comfortable answering."*

Participants will only be evaluated in a private office setting where no one can overhear and they will also be able to request that exercise sessions occur in a similar private setting if that is their preference. Participants will be reminded that they are free to refuse to answer any questions that they do not feel comfortable answering.

## 16.0 Confidentiality

### A. Confidentiality/Security of Study Data

Describe the local procedures for maintenance of security and confidentiality of **study data and any records that will be reviewed for data collection.**

*16.1 Where and how will all data and records be stored? Include information about: password protection, encryption, physical controls, authorization of access, certificates of confidentiality, and separation of identifiers and data, as applicable. Include physical (e.g. paper) and electronic files.*

All paper data collection files will be stored in a locked credenza located in Room 2016 of the IHP ([name] office). This office is locked with key access held by [name] and [name]

(*Vitality* Fitness staff member). All demographic, testing, questionnaire, and exercise data will be electronically stored on the Shared T drive (CR1\app2\Shared\Vitality) in a separate folder which is password protected. Data will be entered into the Shared by [name], [name] and *Vitality* Fitness staff member [name].

*16.2 How long will the data be stored?*

There is no scheduled date at which this information will be destroyed or no longer used. Because this information is a feasibility study, we will continue to use this study to apply for future grants and could be used for and it is not possible to determine when this will be complete.

*16.3 Who will have access to the data?*

[name], [name]

*16.4 Who is responsible for receipt or transmission of the data?*

[name]

*16.5 How will the data be transported/transmitted?*

na

## **B. Confidentiality of Study Specimens**

Describe the local procedures for maintenance of confidentiality of study specimens.

**N/A:** No specimens will be collected or analyzed in this research.  
(Skip to Section 17.0)

*16.6 Where and how will all specimens be stored? Include information about: physical controls, authorization of access, and labeling of specimens, as applicable.*

*16.7 How long will the specimens be stored?*

*16.8 Who will have access to the specimens?*

16.9 *Who is responsible for receipt or transmission of the specimens?*

16.10 *How will the specimens be transported?*

## **17.0 Provisions to Monitor the Data to Ensure the Safety of Subjects**

**N/A:** This study is not enrolling subjects OR is limited to records review procedures only OR is a minimal risk study

17.1 *Describe the plan to evaluate the data periodically regarding both harms and benefits to determine whether subjects remain safe. The plan might include establishing a data safety monitoring committee and a plan for reporting data monitoring committee findings to the IRB and the sponsor.*

17.2 *Describe what data are reviewed, including safety data, untoward events, and efficacy data.*

17.3 *Describe any primary or secondary safety endpoints.*

17.4 *Describe how the safety information will be collected (e.g., with case report forms, at study visits, by telephone calls with participants).*

17.5 *Describe the frequency of safety data collection, including when safety data collection starts.*

17.6 *Describe who will review the safety data.*

17.7 Describe the frequency of review of cumulative safety data.

17.8 Describe the statistical tests for analyzing the safety data to determine whether harm is occurring.

17.9 Describe any conditions that trigger an immediate suspension of the research.

## 18.0 Withdrawal of Subjects

N/A: This study is not enrolling subjects. This section does not apply.

18.1 Describe anticipated circumstances under which subjects may be withdrawn from the research without their consent.

Failure to take part in scheduled visits without notification AND failure to respond to attempts at contact.

18.2 Describe any procedures for orderly termination.

NOTE: Examples may include return of study drug, exit interview with clinician. Include whether additional follow up is recommended for safety reasons for physical or emotional health.

n/a

18.3 Describe procedures that will be followed when subjects withdraw from the research, including retention of already collected data, and partial withdrawal from procedures with continued data collection, as applicable.

If a subject withdraws from the study, their data will be included in the study up to the point of withdrawal.

18.4 Describe what will happen to data already collected.

Data that has already been collected will be stored physically and electronically as stated previously.

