### **1.0 Objectives**

*1.1 Describe the purpose, specific aims, or objectives of this research. Specifically, explain why it is important to do the study.*

Historically, pregnant women were advised to refrain from exercise due to concerns of maternal and fetal risk such as preterm delivery, low infant birth rate and fetal stress. Despite current research that has demonstrated substantial benefits for maternal, fetal, and infant health, only 9-15% of pregnant women meet the current physical activity recommendations. In addition, pregnancy exercise research is confounded by a lack of randomized controlled trials (RCT) that include diversity in participant demographics, specifically inner city populations, and difficulty accurately quantifying weekly exercise volume. We propose a pilot RCT investigating two different approaches to exercise intervention across a spectrum of demographics that we believe will result in improved exercise adherence as well as in maternal and infant health outcomes.

*1.2 State the hypothesis to be tested, if applicable.*

*NOTE: A hypothesis is a specific, testable prediction about what you expect to happen in your study that corresponds with your above listed objectives.*

Specific Aim #1: To determine the feasibility of two types of exercise interventions (supervised & home exercise) in terms of design, implementation and adherence. Our working hypothesis is that both supervised and home exercise interventions will be implementable as designed in pregnant women as evidenced by recruitment, eligibility, retention, follow-up and exercise adherence from 1st trimester through 6-months post-natal at a 60% rate, but that adherence to the two types of exercise interventions will differ by demographic. A secondary exploratory hypothesis is that we will be able to successfully recruit and retain 50% of our pregnant women from the Syracuse Community Health Center (primarily women with lower resources).

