## **5.0 Data Management and Analysis**

*5.1 Describe the data analysis plan, including any statistical procedures. This section applies to both quantitative and qualitative analysis.*

Statistical analysis used to determine feasibility of the exercise intervention will include general descriptive statistics to assess recruitment, eligibility, retention, follow-up and exercise adherence. In addition, we will conduct a survey and interview of subjects related to acceptability to participate in EX and HOMEEX and discuss barriers to regular exercise which will be analyzed using descriptive statistics and a phenomenological approach. To determine the feasibility of maternal and infant outcomes, Kruskal-Wallis and Friedman's ANOVA will be used to investigate between group and within group differences. Relationships between variables will be analyzed using Spearman correlation coefficient. Because this is a feasibility study, the results will be used as preliminary data to apply for future funding and also will provide variable quantitative and qualitative data for validating interventions that can increase adherence to exercise guidelines during pregnancy in women with different ethnic and socioeconomic backgrounds.

*5.2 If applicable, provide a power analysis for the number of subjects to be included. If qualitative research, so state, and provide general justification for the total number of subjects proposed.*

*NOTE: This may not apply to certain types of studies, including chart/records reviews, survey studies, or observational studies. This question is asked to elicit whether the investigator has an adequate sample size to achieve the study objectives and justify a conclusion.*

This is a pilot project aimed to investigate feasibility of approach and appropriateness of maternal outcome measures. If the working hypotheses are supported, the next phase will be a large, randomized intervention study. Pilot data from this project can be utilized in the power analysis for the larger study.

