## **6.0 Local Number of Subjects**

6.1 *Indicate the total number of subjects who will be enrolled or records that will be reviewed through Upstate.*

No more than 18 total participants (six per group)

6.2 *If applicable, indicate your screen failure rate, i.e., how many subjects you expect to screen to reach your target sample.*

54 (anticipate that for every three women screened, one will participate in the study)

6.3 *Justify the feasibility of recruiting the proposed number of eligible subjects within the anticipated recruitment period. For example, how many potential subjects do you have access to? What percentage of those potential subjects do you need to recruit?*

The feasibility of recruitment is part of what is being investigated in this pilot project and findings from this project will inform the recruitment plan of the future large intervention study. The plan for the pilot is to recruit no more than 18 (six per group) low risk pregnant women with a singleton pregnancy from Syracuse Community Health Center (50%), University OB/GYN Associates, and Upstate Community OB/GYN. All women will be enrolled during the 1st trimester (6 to 13-weeks' gestation) and without absolute contraindications to moderate intensity exercise during pregnancy as defined by American College of Sports Medicine (ACSM) and American College of Obstetricians and Gynecologists (ACOG). All participants will be cleared for exercise by their OB/GYN.

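### Friedman's ANOVA, the only within-group method named, omits any woman with an incomplete series, although section 18.3 keeps her data in the study up to withdrawal

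*Combined protocol and SAP*

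**What the plan says.** Section 5.1, repeated in section 11.0, gives the inferential plan for the maternal and infant outcomes: "Kruskal-Wallis and Friedman's ANOVA will be used to investigate between group and within group differences". Read in order, and in line with standard use, Kruskal-Wallis is the between-group test and Friedman the within-group test.

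Section 18.3 covers women who leave: "If a subject withdraws from the study, their data will be included in the study up to the point of withdrawal".

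Section 11.0 sets the questionnaire occasions as a baseline, then "25-26 weeks (late 2nd trimester), and 37-38 weeks (late 3rd trimester), and monthly through 6-months post-natal". That is nine occasions. The treadmill test has three: baseline, and 3 and 6 months after birth.

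Incomplete series are foreseen. Section 1.2 counts as success "follow-up and exercise adherence from 1st trimester through 6-months post-natal at a 60% rate", a threshold that also covers retention. Section 18.1 allows withdrawal of women who cannot be reached, and section 19.4 provides for removal of women who develop an absolute contraindication.

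The documents give no missing-data rule, no analysis set, no list of visits entering Friedman's test, and no method for incomplete series.

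**The concern.** Friedman's test ranks each woman's values across all analysed occasions and has no place for a woman with a gap. Leaving at month 5, or missing one monthly form, removes her whole series from the test, including the visits she attended. That sits badly with an intention to use data up to withdrawal.

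Specific Aim #2 asks whether the measures can detect change over time in the two exercise groups, and section 5.2 makes the larger trial conditional on the working hypotheses being supported. With six women per arm, each omitted woman is one sixth of the arm. A null within-group result could then reflect the shrinking of the test set and not an insensitive instrument.

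**Working it through.** **Plan's own figures.** 3 groups × 6 = 18 women, and 18 × 3 screened per participant = 54. Both reproduce. The plan gives no alpha, power, effect size or dropout allowance, so the rest is scenario work.

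**Inputs from the documents.** Six women per arm (6.1); nine questionnaire occasions, 1 + 2 + 6 (11.0); 60% retention (1.2), used as a scenario.

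**Assumptions.** All nine occasions enter the test. Dropout has a constant hazard over the eight follow-ups and is unrelated to outcome. The test level is 5%.

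**Usable women, dropout alone.** 6 × 0.6 = 3.6 per arm, or 10.8 of 18. About 7.2 women are omitted.

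**Observations left out.** The chance of staying from one visit to the next is h = 0.6^(1/8) = 0.938. Expected visits per woman are the sum of h^j for j = 0 to 8, which is 7.07. Complete series supply 9 × 0.6 = 5.4. Share left out = 1 − 5.4/7.07 = 24%. Timing matters: the share is 7% if all leavers go after baseline (1 − 5.4/5.8), 25% if the last visit is spread evenly over visits 1 to 8 (1 − 5.4/7.2), and 37% if all go after visit 8 (1 − 5.4/8.6).

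**Adding isolated missed visits** (rate m at each follow-up, assumed). The chance of a complete series is 0.6 × (1 − m)^8.

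| m | P(complete) | Women per arm | Observations left out | Arms with fewer than 2 usable |
|---|---|---|---|---|
| 0% | 0.60 | 3.6 | 24% | 4% |
| 5% | 0.40 | 2.4 | 47% | 24% |
| 10% | 0.26 | 1.5 | 64% | 51% |

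The last column is (1 − p)^6 + 6p(1 − p)^5.

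**Three-occasion fitness test.** The smallest exact Friedman p-value is 1/(k!)^(n−1). With k = 3 and n = 2 it is 1/6 = 0.167, so 5% cannot be reached; with n = 3 it is 1/36 = 0.028. At 60% retention the chance that an arm has two or fewer completers is 0.4^6 + 6(0.6)(0.4^5) + 15(0.6^2)(0.4^4) = 0.179. For at least one of three arms it is 1 − (1 − 0.179)^3 = 0.447. At 70% and 80% retention the latter falls to 0.197 and 0.050.

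**Power by simulation.** Arms of six, nine visits, a steady trend across the visits, and within-woman permutation p-values. Friedman uses complete series; Skillings-Mack uses all visits. An arm with fewer than two complete series counts as no rejection for Friedman. Repeated runs gave these ranges:

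| Trend | Missed visits | Friedman | Skillings-Mack |
|---|---|---|---|
| 2 SD | 0% | 0.48–0.50 | 0.56–0.60 |
| 2 SD | 5% | 0.26–0.29 | 0.53–0.56 |
| 2 SD | 10% | 0.13–0.17 | 0.50–0.55 |
| 1 SD | 0% | 0.13 | 0.14 |

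**Check of the tests.** In a simulated 6 × 9 arm with two women truncated, Friedman returned no value. With omission switched on, it returned exactly the result from the four complete women. Skillings-Mack used all six. On the complete data both statistics were 1.467.

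**The case against.** A reader might infer that sections 18.3 and 5.1 flatly contradict each other and that withdrawn women's data are thrown away. The documents do not support that. Section 18.3 answers a form question about keeping data already collected, and it promises inclusion in the study, not in every test. The feasibility descriptives, Kruskal-Wallis at an attended visit and Spearman correlations can all use her data. The loss is to the within-group test only.

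The nine-occasion test is also a reading. The plan does not list the visits, and a test on fewer of them would keep any woman who attended those.

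The 60% is a success threshold, not a dropout forecast. The missed-visit rates and the 2-SD trend are in neither section. Home visits for the HOMEEX and usual-care questionnaires, and weekly or twice-weekly contact, may keep isolated misses low. With dropout alone the gain is modest at 2 SD and negligible at 1 SD.

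It is also tempting to say that the result would be biased towards women who persist. A complete-series test does describe only those women, but the simulation makes dropout unrelated to outcome and so shows no bias.

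Finally, this is an 18-woman pilot with no confirmatory claim. All of this stands. What remains is that the only named within-group method cannot use an incomplete series, the plan expects such series, and nothing else in it deals with them.

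**Conclusion.** The point holds for the within-group test. As written, that test omits every woman with a gap in the analysed visits. On the nine-occasion reading at 60% retention, this means about 3.6 usable women per arm and about 24% of collected questionnaire observations left out (7% to 37% depending on when women leave).

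The power cost depends on assumptions that the documents do not supply. It is about 0.5 against 0.57 for a 2-SD trend with dropout alone, negligible at 1 SD, and about 0.27 against 0.54 if 5% of follow-up visits are also missed. The change is worth making because Aim 2 turns on detecting change and the arms are very small. It does not undermine the descriptive feasibility aim.

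**What to change.** In sections 5.1 and 11.0:

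- State which visits enter the within-group test for each outcome.
- Replace Friedman with the Skillings-Mack test and a within-woman permutation p-value. It is identical to Friedman when data are complete, so nothing is lost if nobody withdraws.
- Include all women with at least two analysed visits, which brings the test into line with section 18.3.
- Report, per arm, the number of women with complete and with partial series.
- Optionally, add change from baseline with 95% confidence intervals from a mixed model with a random effect for woman, as description only. In arms of six these intervals will be wide.

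The cost is wording and a little analysis time, with no new data. There is a small downside. Skillings-Mack assumes that missingness is unrelated to outcome; the mixed model assumes missing at random and a distribution. Neither removes bias if women leave because of how they are doing, and the report should say so.
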